Visit 2 to 3: Upon parent consent in Visit 0 or 1, the child will be assessed on the MSEL and ADOS. However, MSEL assessment may be conducted before informed consent as part of clinical routine practice. They will also be assessed on the Vineland Adaptive Behaviour Scales (VABS) and

¹ Clinic-based intervention sessions are 60 minutes while VC based intervention sessions are 45 minutes. This includes an additional 15 minutes for therapists' administrative and documentation time.

Parenting Stress Index (PSI). Children who meet the criteria for Autism on the ADOS and do not have any of the exclusion criteria will be offered to be part of the study.

Visit 4: On completion of the above assessments, the paediatrician will share the MSEL and ADOS report with parents and confirm enrolment into the study if the child meets the inclusion criteria. If the child does not, they will be referred to standard care outside the study. Children whose parents consent to be on the study will be randomly assigned to either the telerehab program (experimental arm) or standard program (control arm) using block randomisation. The paediatrician will inform parents of the study arm that they are assigned to.

Visit 5a: Initial assessments based on the FSC, Joint Engagement Rating Inventory (JERI), child's routines (parent interview) and Family Early Intervention Quality of life (FEIQoL) will be completed for all. Parents will also participate in a short demographic and cost survey. If parents are unable to complete the surveys during their clinic-based session, they will be sent the surveys through email or asked to answer the questions over a phone call. Parents may also be invited to participate in an (semi structured, in-depth) interview for evaluating the perceived effectiveness of standard care.

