
a. Is the intervention as effective as the standard care model in improving the level of function among children with ASD?
	
Mullen's Scale of Early Learning (MSEL)
	
MSEL is a standardized developmental assessment to examine developmental skills of children aged birth to 68 months on gross motor and cognitive scales using 5 subscales: Gross Motor, Visual Reception, Fine Motor, Expressive Language, and Receptive Language. T scores, percentile ranks, and age equivalents can be computed for the five scales separately.
 
For each scale, the assessment derives a T-score with a mean of 50 and standard deviation of 10, a percentile score, and an age equivalent indicating at what developmental age the child is performing. An early learning composite (ELC) score is calculated from the total of scores on all scales (excepting the gross motor scale) with a mean of 100 and standard deviation of 15. T scores for subscales have a mean of 50 (SD: 10). (Bacon et al,2014)
 
For children suspected of ASD, MSEL is often chosen because of its wide age range and 5 subscales that allow separate assessment of verbal and non-verbal abilities.
 
Previous studies of intervention efficacy has used MSEL subscale scores for greater granularity of analysis, to understand the impact of intervention on specific functions of the child and separate assessment of verbal and non-verbal activities (Vismara et al, 2009).
	
Differences in scores on the subscales of the MSEL from baseline to program conclusion will be calculated and compared between the two intervention groups

	
Vineland Adaptive Behaviour Scales (VABS-III)
	
VABS-III is a standardised assessment tool that utilises a semi-structured interview format to measure adaptive behavior. The main domains are: Communication, Daily Living Skills and Socialization. The Vineland-III is used for measuring an individual's daily functioning, progress planning and monitoring.
	
Differences in scores on VABS-III in communication, socialisation and daily living from baseline to program conclusion will

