
Is the tele-health intervention as effective as standard care in improving parental stress?
	
Short Form (PSI-SF)
	
relationship. The questionnaire is meant for parents of young children, and can be used for the parents of children 0-12 years of age. Each item requires the parent/caregiver to rate the degree to which s/he agrees with a statement on a five-point Likert scale (1 = Strongly Agree, 2 = Agree, 3 = Not Sure, 4 = Disagree, and 5 = Strongly Disagree). The questionnaire's 36 items are divided into three subscales: Parental Distress (PD), Parent-Child Dysfunctional Interaction (P-CDI), and Difficult Child (DC). Items are scored and added together to establish a total score as well as three subscale scores.
 
The PSI-SF produces subscale raw scores ranging from 12 to 60 and an overall Parenting Stress (PSI-PS) total score that ranges from 36 to 180; a higher score indicates a greater level of stress. A PSI-PS score above 85 (at the 90th percentile) indicates clinically significant parenting stress (Abidin, 1995).
	
parental distress, parent-child dysfunctional interaction and difficult child will be tracked by calculating the change in raw scores on the PSI-SF from baseline to program conclusion and compared between the two intervention groups

d. Is the tele-health intervention as effective as standard care at improving child outcomes over the long term and various contexts?
	
Mullen's Scale of Early learning (MSEL) Early learning Composite (ELC)
	
For each scale, the assessment derives a T-score with a mean of 50 and standard deviation of 10, a percentile score, and an age equivalent indicating at what developmental age the child is performing. An early learning composite (ELC) score is calculated from the total of scores on all scales (excluding the gross motor scale) with a mean of 100 and standard deviation of 15. T scores for subscales have a mean of 50 (SD: 10) (Bacon et al., 2014).
 
Early learning composite score has also been widely used as a score to compare effectiveness of early intervention programs (Shank 2011, Bishop et al., 2011).
	
Differences in ELC score from baseline to program conclusion will be calculated and compared between intervention groups

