Protocol deviation is defined as any divergence from what was pre-planned and approved by the institutional review board. As the study is conducted as part of routine care and operations, there are practical constraints that may cause protocol deviations to occur. Rescheduling of appointments by the parents (e.g. due to work constraints, child's sickness, other events) or defaulting appointments is inevitable. Hence, for per-protocol analyses, we will only exclude participants with major protocol deviation, which will be defined as participants who do not complete 80% of the intended therapy sessions allocated for their study arm. This means that a control arm participant must attend at least 8 out of 10 clinic-based sessions. For the remaining 2 sessions, participants can either be attending it through video-conferencing (due to the COVID-19 pandemic) or miss the appointment.

Quantitative Outcomes

For the randomized trial, since the study is a non-inferiority study, statistical analysis will be carried out on a per-protocol basis. Subjects with any major protocol deviation as defined above will be excluded from the final analysis.

All demographic, clinical and cost characteristics will be analysed descriptively. Mean (SD) or median (range), whichever is more appropriate will be reported for numerical variables, while N (%) will be reported for categorical variables. 2-sample t-tests, or Mann-Whitney U tests will be used to compare the change of MSEL score between 2 arms. Mean difference and 95% CI will be estimated. If the lower boundary of the 95% CI is more than -5, non-inferiority will be declared. Changes in the quality of parent-child engagement, parental stress index score, and adaptive score will be compared by using either a 2-sample t-test, or a Mann-Whitney U test, whichever is more appropriate. Linear regression will be used to adjust for any covariates.

Cost-Effectiveness Analysis

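### Name one estimate, ANCOVA of final MSEL on arm and baseline MSEL, as the one compared with -5; the plan's regression sentence gives no covariate and no role.

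*Combined protocol and SAP*

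**What the plan says.** Under Quantitative Outcomes, "2-sample t-tests, or Mann-Whitney U tests will be used to compare the change of MSEL score between 2 arms". A mean difference with a 95% CI is then estimated, and the decision rule follows: "If the lower boundary of the 95% CI is more than -5, non-inferiority will be declared". After the secondary comparisons comes one sentence on adjustment: "Linear regression will be used to adjust for any covariates". It gives no covariate, no form of the outcome and no role. Table 2 of the cost-effectiveness section leaves the same choice open, since its outcome estimates may come from a t-test or a regression.

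The analysis set is per protocol: "Subjects with any major protocol deviation as defined above will be excluded from the final analysis".

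On timing, the Visit 2 to 3 entry under Baseline Assessments says "the child will be assessed on the MSEL and ADOS". Random assignment comes at Visit 4, where "The paediatrician will inform parents of the study arm that they are assigned to". Annex 1 shows the same order.

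The deciding score is not fixed. Sample Size Calculation refers only to an MSEL score. In the Indicators and Outcomes table, question (a) uses "Differences in scores on the subscales of the MSEL from baseline to program conclusion" and question (d) uses "Differences in ELC score from baseline to program conclusion". The cost-effectiveness Outcomes section calls the Early Learning Composite (ELC) the primary outcome.

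**The concern.** There are two linked problems.

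1. **Efficiency.** Subtracting baseline fixes its coefficient at 1. ANCOVA estimates that coefficient, so in large samples its residual variance is never larger and is usually smaller. In a non-inferiority trial a narrower interval feeds directly into the decision.
2. **An open choice.** An adjusted mean difference also fits the wording of the decision rule. The adjusted and unadjusted estimates differ by (1 - slope) times the baseline difference between arms. Because the analysed set is per protocol, randomisation does not guarantee baseline balance in it, and the two may differ by more than chance. Unless one is named in advance, the more favourable could be chosen.

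The Mann-Whitney option adds to the uncertainty, because the usual test of no difference does not address a margin of -5. The unsettled score matters too. Five points is one third of an SD on the ELC (5/15) but half an SD on a subscale T-score (5/10).

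**Working it through.** **Inputs from Sample Size Calculation:** SD of change 15, true difference +1.5, margin 5, one-sided 5%, 80% power, 66 per arm before losses, 100 per arm recruited. **From Quantitative Outcomes:** lower 95% limit above -5, which is one-sided 2.5%. **Assumed, not in the documents:** rho, the baseline-final correlation, and k, the final SD divided by the baseline SD.

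**Plan's own figure.** n per arm = 2 x (15 x (1.6449 + 0.8416)/6.5)^2 = 65.85, so 66 per arm and 132 in total. This reproduces. Under the 95% CI rule the same formula with 1.96 gives 83.6, so 84 per arm.

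**Variances.** With the SD of change held at 15:

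- baseline variance sB^2 = 225/(1 + k^2 - 2 rho k)
- ANCOVA residual variance = k^2 sB^2 (1 - rho^2)
- within-arm slope = rho k
- change-score variance minus ANCOVA variance = sB^2 (1 - rho k)^2

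The last quantity is never negative and is zero when rho k = 1.

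**Power** = Phi(6.5/(SD x sqrt(2/n)) - 1.96). Unadjusted at n = 66: 6.5/(15 x 0.1741) - 1.96 = 0.529, giving 70.2%. At n = 100 it is 86.5%. For ANCOVA:

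| rho | n=66, k=1 | n=66, k=1.2 | n=100, k=1 | n=100, k=1.2 |
|---|---|---|---|---|
| 0.3 | 87.0% | 81.4% | 96.7% | 93.9% |
| 0.5 | 82.0% | 76.0% | 94.3% | 90.7% |
| 0.7 | 77.0% | 71.6% | 91.4% | 87.6% |
| 0.8 | 74.7% | 70.3% | 89.8% | 86.6% |
| 0.9 | 72.4% | 71.2% | 88.2% | 87.3% |

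**Gap between the estimates.** Let dF and dB be the arm differences at final and baseline, and b the slope. The change estimate is dF - dB and the ANCOVA estimate is dF - b dB, so they differ by (1 - b) dB. For dB = 3 the gap is 1.5 points at b = 0.5, 0.9 at b = 0.7 and 0.12 at b = 0.96, which is 30%, 18% and 2% of the margin. By chance alone, at rho 0.5 and k = 1, dB has SD 15 x sqrt(2/66) = 2.61.

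**Error if either interval may decide.** Simulation with bivariate normal scores, 66 per arm, t-based 95% CIs, true difference -5 and 200,000 trials per cell. Each analysis alone declares non-inferiority in 2.5%. Either one declares it in:

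- k = 1: 3.8/3.7/3.4/3.3/3.0% for rho 0.3/0.5/0.7/0.8/0.9
- k = 1.2: 3.7/3.4/2.9/2.7/2.8%

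**At the planned difference of +1.5** (k = 1, 40,000 trials), most disagreement is the power gain itself. ANCOVA alone succeeds in 18.5/13.7/9.2/6.7/4.2% of trials, and the change score alone in 1.8% to 2.5%.

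**The case against.** The strongest reply is that the plan already identifies its estimate. The t-test, the mean difference, the CI and the -5 rule come in sequence, and the regression sentence follows the secondary outcomes with no decision rule attached. On that reading the favourable-choice simulation models conduct the plan does not allow. This stands in part: those error rates are an upper bound on a residual ambiguity, and they stay below the 5% used for sizing. The words still do not exclude an adjusted interval.

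Second, the gain is uncertain. Holding the SD of change at 15 with k = 1 implies baseline SDs of 15/sqrt(2(1 - rho)) = 19.4, 23.7 and 33.5 at rho 0.7, 0.8 and 0.9, against an ELC norm of 15. If the score SD is held at 15 instead, the SD of change is 11.6 at rho 0.7 and 9.5 at rho 0.8. Unadjusted power at 66 per arm is then 90% and 98%, and ANCOVA adds about 4 points and 1 point. This stands as a limit on size. At rho 0.5 and k = 1 both SDs equal 15, and the comparison is 82% against 70%.

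Third, 66 per arm means losing 34% of the 100 recruited. Under the 95% CI rule the unadjusted analysis falls below 80% power only if more than 16% are lost or excluded. That is correct, and it is why the 100-per-arm figures are shown.

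Fourth, if exclusions make baseline differences systematic, neither estimate is generally unbiased. That is also correct. It supports naming one estimate in advance, and it is not an argument that ANCOVA repairs selection.

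**Conclusion.** The concern holds. The plan gives regression neither a covariate nor a role, while a baseline MSEL taken before allocation is available and the -5 margin carries over unchanged to the ANCOVA arm coefficient.

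The benefit runs from nil to about 17 percentage points of power at 66 per arm (70% to 87%) and from nil to about 10 at 100 per arm (86.5% to 96.7%). It depends on rho and k, which the documents do not give, and on the SD of change being 15. Under a fixed score SD of 15 the gain at high correlation is only a few points. There is no large-sample precision loss in any of these cases. Closing the open choice removes at most 0.2 to 1.3 percentage points of excess error over 2.5%.

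The trial can be interpreted without this change, but the decision rule is underspecified and easily completed. ANCOVA does not cure selection from the per-protocol exclusions. Nor does it cure the separate mismatch between sizing at one-sided 5% and deciding on a 95% CI.

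**What to change.** Amend Quantitative Outcomes to state the following:

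- The primary analysis is linear regression of final MSEL on arm and baseline MSEL, and only the lower 95% limit of this adjusted difference is compared with -5.
- The unadjusted comparison of change and any rank test are sensitivity analyses.
- One named MSEL score decides, with Sample Size Calculation, questions (a) and (d) of the Indicators and Outcomes table, and the cost-effectiveness Outcomes section reconciled to it.
- Whether MSEL results by arm have been seen. Table 3 scheduled a preliminary analysis of Year 1 data in Year 2. If they have been seen, the unadjusted estimate remains the deciding one and ANCOVA is a sensitivity analysis.
- VABS and PSI are adjusted in the same way for their Visit 2-3 baselines. JERI and FEIQoL baselines are taken at Visit 5a, after families learn their arm at Visit 4, and this should be stated as a limitation.

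**Cost.** No new data or visits. The combined protocol is at Version 8 (19/08/2022), so the change needs an amendment and DSRB approval as described under Research Ethics, made before MSEL outcomes by arm are examined. Table 4 shows no enrolment in Year 5, so the amendment also needs a short justification alongside the data-access statement.

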		VABS-III provides a measure of adaptive skills used to cope with challenges of daily living. A caregiver completes a questionnaire regarding the individual's current level of functioning across three domains: communication, daily living skills and socialization. The Vineland Scales are applicable to children with and without delays from birth to 18 years, 11 months. All scales use standard scores with a mean of 100 and a standard deviation of 15, a percentile score, and an age equivalent indicating at what developmental age the individual is performing. Scores on the three domains are combined to obtain an overall adaptive behavior composite (ABC) with a mean of 100 and a standard deviation of 15.	be calculated and compared between the two intervention groups
b. Is the tele-health intervention as effective as standard care in improving parent-child interaction?	Joint Engagement Rating Inventory (JERI)	
JERI measures:
 
 - joint engagement, - communication dynamics and - shared topics in a caregiver-child interaction on a 7-point likert scale (Adamson & Bakeman, 2012). 
This is a structured assessment of joint attention and communication. It measures multiple aspects of caregiver-child interactions and identifies the specific triadic elements in engagement which are effected in Autism. This has the advantage of being a standardized assessment of social communication. It provides an insight into the dynamics of caregiver child interactions which will help in intervention planning to enhance the quality of caregiver-child engagement.
	
Change on the JERI will be tracked by calculating the changes in:
 
 - nature of joint engagement, - child's participation in joint engagement with caregiver, - caregiver behaviours during engagement and - the range and quality of the caregiver-child interactions 
from baseline to program conclusion and compared between the two intervention groups

c.	Parenting Stress Index-	PSI-SF (Abidin, 1995) is an abbreviated version of the PSI. It is a 36-item self-report questionnaire assessing the level of relative stress in a parent-child	Change on the PSI-SF across 3 domains:

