Patients will be recruited for the program after obtaining a preliminary diagnosis of ASD from the developmental paediatrician. ADOS-2 will be administered to confirm the diagnosis and thus participation in the research study. We will not be advertising this study to the public.

Pilot

An initial pilot feasibility study with 6 children and families will be conducted at the start of the project to identify any practical issues or weaknesses in the program or protocol before full scale evaluation.

Sample Size Calculation

The randomized trial is designed as a non-inferiority study to compare the changes in MSEL between 2 interventions. We expect that the change in MSEL score for the subjects in the new intervention arm will be slightly better than that in the control arm by 1.5 units. Assuming the SD of changes in MSEL score is 15 units, with 5 units as the non-inferiority margin, based on a one-sided test with 80% power and 5% significance level, it is sufficient to recruit 132 subjects (66 in each arm). We decided to recruit 200 subjects in total (100 in each arm) after considering withdrawals and lost to follow up. The computation was performed using a proprietary software programmed in R.

Randomisation Process and Blinding

Computer-generated randomisation will be used to randomly assign the participants to one of the intervention groups. Block randomisation will be used to allocate the recruited subjects into one of the interventions. A randomisation list will be generated by the study statistician and envelopes will be prepared. Although the allocation of intervention will be concealed and the study team will not know in advance which subject will receive which intervention, the blinding will not be possible once the intervention is assigned. Assessors of the initial and final MSEL were not told of the intervention status of the patient to avoid bias in outcome assessment. Blinding of the parents is not possible in the context of this study. Phone calls will be made if necessary to confirm appointments and/or before commencing consultation over video conference in the Telerehab group. Parents in both study arms will be encouraged to spend 2h per week in quality interactions with their children.

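### VABS-III, JERI and PSI-SF are asked an as-effective-as question but given only a test of no difference, and the plan does not say how a non-significant result will be read; FEIQoL has no named analysis

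*Combined protocol and SAP*

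**What the plan says.** The Indicators and Outcomes table words its effectiveness questions in non-inferiority terms:

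- Row a (MSEL subscales and VABS-III): "Is the intervention as effective as the standard care model in improving the level of function among children with ASD".
- Row b (JERI): "Is the tele-health intervention as effective as standard care in improving parent-child interaction".
- Row c (PSI-SF): "Is the tele-health intervention as effective as standard care in improving parental stress".
- Row f asks the same of family quality of life, measured by FEIQoL.

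The Sample Size Calculation section ties the design to one instrument: "The randomized trial is designed as a non-inferiority study to compare the changes in MSEL between 2 interventions". The Quantitative Outcomes section then declares non-inferiority if the lower bound of the 95% CI for the MSEL difference lies above -5. The next sentence turns to parent-child engagement, parental stress and adaptive score, and says that changes in these "will be compared by using either a 2-sample t-test, or a Mann-Whitney U test, whichever is more appropriate". It gives them no margin, direction of benefit, interval or rule for drawing a conclusion. A closing sentence adds linear regression for covariates, without naming the covariates.

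FEIQoL is not mentioned in the Quantitative Outcomes section. Row f says only that changes in its four areas will be compared between groups.

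**The concern.** A t-test or Mann-Whitney test takes no difference as its null hypothesis. Failing to reject that null is weak evidence of similarity, and the weaker the data, the easier it is to obtain. The plan applies the right logic to MSEL, where the interval must exclude a stated loss, but not to the other outcomes that are asked the same kind of question. A Mann-Whitney p-value on its own also gives no mean difference with an interval for a reader to judge.

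At stake is how the secondary results will be worded. The per-protocol analysis drops participants who complete less than 80% of their sessions. That shrinks the sample and makes non-significance more likely. The wording also matters for the economic analysis: the Cost-Effectiveness Analysis section rests on whether telerehab saves cost, because the trial is one of non-inferiority, and it names VABS and JERI as outcomes beside MSEL. Only MSEL has a rule for showing that outcomes are not worse.

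**Working it through.** **1. The plan's own figure.** The Sample Size Calculation section supplies these inputs: "Assuming the SD of changes in MSEL score is 15 units, with 5 units as the non-inferiority margin"; telerehab expected to be "slightly better than that in the control arm by 1.5 units"; and a calculation "based on a one-sided test with 80% power and 5% significance level".

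n per arm = 2 × SD² × (z₀.₉₅ + z₀.₈₀)² / (margin + advantage)²
= 2 × 15² × (1.645 + 0.842)² / (5 + 1.5)²
= 65.8, rounded up to 66, or 132 in total.

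This matches the stated 132, which is a calculation for MSEL only. The documents give no margin and no SD of change for VABS, JERI, PSI-SF or FEIQoL, so no corresponding sample size can be derived for them.

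**2. How often a difference test misses a real deficit.** VABS is used as the example.

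Inputs:
- True deficit d = 5 points. This is an assumption, chosen because it equals the MSEL margin.
- SD of change = 15. This is also an assumption: the table's 15 for VABS is the norming SD of the score, not an SD of change. SDs of 10 and 20 show the range.
- n = 66 per arm (the calculated number) and n = 100 per arm (the recruitment target).
- Two-sided 5% test, normal approximation.

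Formulas:
- SE = SD × √(2/n)
- P(non-significant) = 1 − [Φ(d/SE − 1.96) + Φ(−d/SE − 1.96)]

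| SD of change | n per arm | SE | d/SE | P(non-significant) |
|---|---|---|---|---|
| 10 | 66 | 1.741 | 2.872 | 18% |
| 10 | 100 | 1.414 | 3.536 | 6% |
| 15 | 66 | 2.611 | 1.915 | 52% |
| 15 | 100 | 2.121 | 2.357 | 35% |
| 20 | 66 | 3.482 | 1.436 | 70% |
| 20 | 100 | 2.828 | 1.768 | 58% |

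The noncentral t gives nearly the same results: at SD 15, 52.4% and 35.0%.

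**3. What an interval shows instead.** At SD 15 the half-width of the two-sided 95% CI is 1.96 × 2.611 = 5.1 points with 66 per arm, and 1.96 × 2.121 = 4.2 points with 100. With 66 per arm, an observed difference of zero would still be compatible with a loss of about 5 points. The p-value alone hides this.

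**4. Whether the MSEL rule could simply be extended.** It could not. JERI is rated on a 7-point scale, so a 5-unit margin has no sensible meaning there. PSI-SF runs the other way, with higher scores meaning more stress, so a rule on the lower bound would test the wrong side.

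**The case against.** The strongest reply is that these are supportive outcomes on which the trial is not sized, that such outcomes often have no margins of their own, and that estimates are partly planned already. Linear regression yields an adjusted difference and ordinarily an interval. Table 2 of the cost-effectiveness methods draws on t-test or regression estimates for MSEL-ELC, VABS and/or JERI. The MSEL text itself pairs the same two tests with a mean difference and CI. This stands in part: naming the tests does not rule out an interval. But the plan does not commit to reporting one for these outcomes, does not name baseline as a covariate, and does not say how the results will be interpreted. PSI-SF is not among the Table 2 outcomes.

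A reader might also infer four stronger things that the documents do not support:

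- **That the sponsor intends to read p>0.05 as equal effectiveness.** No section says so. The plan is silent, which leaves a risk open but states no intention.
- **That FEIQoL too is given a difference test.** It is not in the sentence that names the tests. Its gap is a missing analysis.
- **That VABS-III is a primary endpoint because it sits under the column headed as primary indicators.** That column covers every row, including satisfaction and costs. The sample size rests on MSEL, and the Outcomes section of the cost-effectiveness methods names the MSEL composite as the primary outcome.
- **That -5 can serve as the VABS margin because VABS and the MSEL composite share a norming SD of 15.** A shared norming SD does not show that a 5-point loss is equally tolerable on both instruments, and the documents justify no VABS margin.

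**Conclusion.** The mismatch between question and analysis is real for VABS-III, JERI and PSI-SF: the planned test cannot deliver the conclusion that the question asks for. For FEIQoL the question is posed and no analysis is named.

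The size depends on assumptions, because the documents give no SD of change for any of these outcomes. For a true 5-point VABS deficit, the chance of a non-significant result runs from 18% (SD 10) to 70% (SD 20) with 66 per arm, and from 6% to 58% with 100 per arm. At SD 15 it is 52% and 35%. No comparable figures on their own scales can be given for JERI, PSI-SF or FEIQoL.

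The primary MSEL non-inferiority conclusion is unaffected. The point concerns what may be claimed from the secondary outcomes and should be settled before the final analysis.

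**What to change.** In the Quantitative Outcomes section:

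1. For VABS-III, JERI, PSI-SF and FEIQoL, make the analysis a baseline-adjusted (ANCOVA) difference in means between arms with a two-sided 95% CI. This also supplies the missing FEIQoL analysis.
2. State the direction of benefit for each outcome, noting that a higher PSI-SF score is worse.
3. State that these outcomes are supportive, that conclusions rest on the interval, and that p>0.05 will not be reported as showing that telerehab is as effective as standard care.
4. Do not carry the -5 MSEL margin over to VABS unless the sponsor justifies it separately for that scale.

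The cost is a few lines of text, with the data already being collected and no change to sample size. The drawback is that some secondary conclusions will have to be reported as inconclusive.
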